### **14.0 BIOSTATISTICS**

The primary objective of this protocol is to assess the safety of whole lung IMRT following standard treatment in patients with synovial sarcoma and lung metastases. To this end we will enroll 15 eligible patients which will take about 6 years. Due to this long enrollment time the safety endpoint

will include both acute (<=3 months from the end of WLI) and late toxicities (>3 months from the end of WLI). Namely, we will evaluate the rate of any grade 3 toxicities (including pneumonitis, esophagitis, pericarditis and cardiac dysfunction) by using Kaplan-Meier estimation. If a patient withdraws from the protocol (expected to be 10% within 1 year), or dies without any grade 3 toxicities (expected to be 50% at 1 year) he/she will be regarded as a censoring at such time points. We will not use a competing risks analysis because it is expected that the withdrawal and death are independent from toxicities, and the actuarial estimate is believed to be more illustrative of the toxicity profile than the cumulative incidence rate by regarding death as a competing risk. For the decision rule we will look at the 1-year toxicity rate. If, the higher bound of the 85%, 1-sided confidence interval of the 1-year toxicity rate based on the (one minus) Kaplan-Meier estimate is lower than 0.25 than we will declare the whole lung IMRT procedure safe. This unusually high type 1 error rate, 15%, is used due to the rareness of such patients and the high progression/mortality rate without WLI. To roughly assess the power of the study with 15 patients, we simulated 10,000 datasets based on the above assumptions and examine the 1-year toxicity rate by Kaplan-Meier method. The following table shows probabilities of claiming whole lung IMRT safety under various values of the true 1-year toxicity rate.

True 1-year toxicity rate	0.05	0.10	0.15	0.20	0.25	0.30	0.35
Probability of claiming whole lung IMRT safe	0.894	0.712	0.536	0.364	0.243	0.154	0.094

As mentioned in Section 11.0, this study is also subject to early stopping if any radiation-related acute toxicities of grade 4 or higher are observed among the patients. If one of these events is observed in one patient, then the protocol will be closed to further accrual until reviewed by the principal investigator in conjunction with the investigators of the study.

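### The safety rule has no provision for zero events: the Kaplan-Meier upper bound then has no width, and the rule returns safe however few patients were followed

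*Combined protocol and SAP*

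**What the plan says.** Section 14.0 plans a single arm: "To this end we will enroll 15 eligible patients which will take about 6 years". Grade 3 toxicity, acute and late together, is to be estimated "by using Kaplan-Meier estimation" and read at 1 year. The decision rule begins "If, the higher bound of the 85%, 1-sided confidence interval of the 1-year toxicity rate based on the (one minus) Kaplan-Meier estimate" and continues "is lower than 0.25 than we will declare the whole lung IMRT procedure safe".

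The plan gives the level as 15%: "This unusually high type 1 error rate, 15%, is used due to the rareness of such patients". Withdrawals ("If a patient withdraws from the protocol (expected to be 10% within 1 year") and deaths without grade 3 toxicity (50% expected at 1 year) are both censored. Operating characteristics come from 10,000 simulated datasets: "The following table shows probabilities of claiming whole lung IMRT safety under various values of the true 1-year toxicity rate". The printed probabilities for true rates of 0.05 to 0.35 are 0.894, 0.712, 0.536, 0.364, 0.243, 0.154 and 0.094.

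Section 14.0 does not name a variance formula or a transformation, does not say what to do when no event occurs, and sets no minimum number at risk at 1 year. Section 13.0 adds no safeguard: it counts every enrolled patient given any lung irradiation, with no minimum follow-up.

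**The concern.** A Kaplan-Meier interval takes its width from the observed events. With no event there is no width, whether 15 patients were followed for a full year or three for a month. The rule then compares 0 with 0.25 and passes automatically.

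Two things are at stake. The first is the reported result. A trial with no grade 3 toxicity would publish an upper bound of 0% from 15 patients, more than half of them expected to be censored before 1 year. The second is the verdict if accrual falls short in this rare disease. A handful of patients with no event would meet the rule, although they could not exclude a rate above 25%.

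**Working it through.** **Inputs, all from Section 14.0.** n = 15; death 50% and withdrawal 10% by 1 year, both censored; one-sided 85% bound (z = 1.036); threshold 0.25. The plan names no time distribution, so exponential times are an assumption of this check.

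**Step 1: reproduce the plan's table.** The upper bound is 1 − S(1) + 1.036 × SE, where SE = S(1) × √Σ[d/(r(r − d))] (Greenwood). 200,000 simulated trials were run per rate.

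| True rate | Plan | Plain, zero events = safe | Log, zero events = safe | Plain, zero events not safe |
|---|---|---|---|---|
| 0.05 | 0.894 | 0.884 | 0.886 | 0.292 |
| 0.10 | 0.712 | 0.705 | 0.711 | 0.366 |
| 0.15 | 0.536 | 0.520 | 0.529 | 0.330 |
| 0.20 | 0.364 | 0.365 | 0.374 | 0.262 |
| 0.25 | 0.243 | 0.243 | 0.251 | 0.187 |
| 0.30 | 0.154 | 0.154 | 0.159 | 0.125 |
| 0.35 | 0.094 | 0.091 | 0.096 | 0.078 |

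Plain and log bounds fit within 2 percentage points in every cell, provided zero-event trials count as safe. A log-log bound with zero events counted as safe does not fit (0.78 at 5%).

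**Step 2: the zero-event bound.** With every d = 0, the Greenwood sum is 0 and S(1) = 1. The plain and log bounds are therefore 0%. The log-log form needs log(−log 1), which does not exist.

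**Step 3: how often this happens.** Yearly hazards are −ln(1 − p) for toxicity, ln 2 = 0.693 for death and −ln 0.9 = 0.105 for withdrawal. The chance that one patient has an observed toxicity within a year is q = (toxicity hazard / total hazard) × (1 − exp(−total hazard)).

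- p = 0.05: q = (0.0513/0.8498) × (1 − 0.4275) = 0.0346, so P(no event) = 0.9654^15 = 0.59.
- p = 0.10: q = 0.0694, so P(no event) = 0.34.
- p = 0.25: q = 0.1755, so P(no event) = 0.055.

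No event is the single most likely count only below a true rate of about 9%. At 10%, exactly one event is more likely (0.38 against 0.34). Zero-event trials are 0.59/0.884 = 67% of safe verdicts at a true 5%, and 0.34/0.705 = 48% at 10%.

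**Step 4: what an exact bound would say.** With no event in Y person-years and a constant hazard, the 85% upper bound is 1 − exp(−1.897/Y), where 1.897 = −ln 0.15. Ignoring toxicity, expected follow-up within 1 year is 15 × (1 − 0.45)/0.7985 = 10.3 person-years, giving 1 − exp(−1.897/10.3) = 17%. The simulated 5th to 95th percentile range is 14% to 21%. To fall below 0.25, Y must exceed 1.897/(−ln 0.75) = 6.59 person-years.

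Using only the m patients at risk at 1 year, the bound is 1 − 0.15^(1/m): 24% for m = 7 and 27% for m = 6. Expected m is at most 15 × 0.5 × 0.9 = 6.75. Among zero-event trials, m is below 7 in about 47% at a true 5% and about 60% at 25%.

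**Step 5: effect on the verdict at n = 15.** Only the zero-event case is altered.

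| True rate | Rule as reproduced | Person-time bound governs | Number-at-risk bound governs |
|---|---|---|---|
| 0.05 | 0.880 | 0.877 | 0.601 |
| 0.10 | 0.705 | 0.703 | 0.537 |
| 0.25 | 0.244 | 0.243 | 0.211 |

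These are separate runs of 40,000 trials, hence the third-decimal differences from Step 1.

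**Step 6: short accrual.** At a true 25%, the rule returns safe with probability 0.24 at n = 15, 0.30 at n = 10, 0.38 at n = 5 and 0.56 at n = 3. At n = 5 every safe verdict is a zero-event trial (0.8245^5 = 0.38), with a person-time bound of about 44%. Five patients can supply at most 5 person-years, below 6.59, so with the person-time bound the probability is 0.

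**The case against.** The strongest reply is that at the planned 15 patients the defect changes almost no decision: about 99% of zero-event trials would also pass the person-time bound. That stands. At full accrual the gain is in what is reported. Several stronger readings are tempting, and the documents do not support them.

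- **A reader might infer that the table proves a 0% bound was used.** It does not. The 0% bound and the person-time bound give 0.880 and 0.877 at a true 5%, which the table cannot tell apart. It shows only that zero-event datasets were nearly all counted as safe. The interval type is itself inferred, and the fit is imperfect: at 0.15 the plan has 0.536 against 0.520 or 0.529.
- **A reader might infer that the zero-event collapse explains why the table gives 0.243 at a true 25% while the text states 15%.** It supplies only about 5.5 of those 24.3 points. Trials with at least one event contribute 18.7, already above 15. The main cause is poor coverage of the plain or log bound at this sample size. The table itself is not miscalculated.
- **A reader might infer that zero events is the expected result whenever the treatment is safe.** That holds only below a true rate of about 9%, whereas the plan's threshold is 25%.
- **A reader might infer that the rule always gets easier as information shrinks.** From n = 15 to n = 5 the probability of a safe verdict falls from 0.88 to 0.84 at a true 5% and stays near 0.70 at 10%. It rises at the higher rates, where the error matters.

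Five patients is also not the planned trial. The accrual halt in Sections 11.0 and 14.0 is triggered by a grade 4 or higher toxicity, so it is not a route to a zero-event trial. Slow accrual, or the discretionary termination allowed in Section 4.2, would be.

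**Conclusion.** The concern holds in a limited form. Section 14.0 has no provision for zero events, and following its rule then gives a bound of 0% or none at all, with a safe verdict that does not depend on follow-up. The outcome is plausible: probability 0.59 at a true 5% and 0.34 at 10%, with about 6 to 7 patients at risk at 1 year and an exact person-time bound near 17%. At 15 patients the consequence is an invalid reported bound rather than a wrong decision. Verdicts change mainly if accrual falls well short.

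The event probabilities rest on the plan's death and withdrawal rates, independent censoring as the plan assumes, and exponential times, which the plan does not state. The 0% bound rests on a plain or log Greenwood interval, inferred from reproducing the table. The person-time figure also rests on a constant toxicity hazard, a real assumption when acute and late toxicity are pooled.

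**What to change.** In Section 14.0, name the variance formula and transformation used when events occur, and add wording such as: *If no event is observed, the governing upper bound is 1 − exp(−1.897/Y), where Y is the total person-years of follow-up within 1 year. A bound of 0% is neither reported nor used. The number at risk at 1 year is reported with the verdict. The bound 1 − 0.15^(1/m), with m at risk at 1 year, is reported as a descriptive sensitivity figure and does not govern.* Then re-run the table under this rule.

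Saying which bound governs matters, because the two often fall on opposite sides of 0.25.

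The cost is analysis wording and a new simulation run, with no added patients or visits. The reported zero-event bound becomes about 17% (14% to 21%) instead of 0%, and its validity depends on a constant hazard. At 15 patients the probability of a safe verdict falls by about 0.3 percentage points or less. With six or fewer patients, at most 6 person-years, a zero-event trial could not be declared safe at any true rate. If the sponsor prefers to avoid the constant-hazard assumption and lets the number-at-risk bound govern, the price is much higher: the probability of a safe verdict at a true 5% falls to about 0.60.

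This change does not bring the error at a true 25% down to 15%. It stays near 0.24, and that needs its own correction.

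### The safety rule is said to have a 15% type I error, but the plan's own simulation table puts it at 24.3%, and the interval method is not named

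*Combined protocol and SAP*

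**What the plan says.** Section 14.0 (Biostatistics) enrols 15 patients and estimates time to grade 3 toxicity by Kaplan-Meier. Withdrawal (10% within 1 year) and death without grade 3 toxicity (50% at 1 year) are treated as independent censoring.

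The decision rule uses the "higher bound of the 85%, 1-sided confidence interval of the 1-year toxicity rate based on the (one minus) Kaplan-Meier estimate"; if this "is lower than 0.25 than we will declare the whole lung IMRT procedure safe". On the error rate the section says: "This unusually high type 1 error rate, 15%, is used due to the rareness of such patients". It adds the high rate of progression and death without treatment as a further reason.

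The operating characteristics follow: "we simulated 10,000 datasets based on the above assumptions". The row headed "Probability of claiming whole lung IMRT safe" reads:

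| True 1-year rate | 0.05 | 0.10 | 0.15 | 0.20 | 0.25 | 0.30 | 0.35 |
|---|---|---|---|---|---|---|---|
| Declared safe | 0.894 | 0.712 | 0.536 | 0.364 | 0.243 | 0.154 | 0.094 |

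The section does not call 15% nominal and does not remark on the 0.25 column. It gives no variance formula, no scale for the bound (plain, log, log-log) and no rule for data with no events.

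**The concern.** The error to control here is declaring the treatment safe when the true 1-year rate is at or above 0.25. The chance of that is greatest at 0.25 itself, so the 0.25 column is the type I error. It reads 0.243, and the text says 15%. The table comes down to about 15% (0.154) only at a true rate of 0.30.

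The 15% figure carries weight. The plan presents it as a deliberate relaxation and defends it on grounds of rarity and prognosis. Anyone who accepts that argument has accepted about a 1 in 7 risk of a false safety claim on the primary endpoint, while the design carries about 1 in 4.

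The unnamed interval method is a second gap, because different bounds at the same 85% level can give different verdicts on the same data.

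**Working it through.** **Inputs, all from Section 14.0.** n = 15; death 50% and withdrawal 10% at 1 year, independent of toxicity; one-sided 85% bound, z = 1.036; limit 0.25; 10,000 simulated data sets. **Assumed:** exponential times (the plan gives only 1-year rates; uniform times gave nearly the same values), and data with no events counted as safe.

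**1. Is the gap simulation noise?** The standard error of the printed figure is √(0.243 × 0.757 / 10,000) = 0.0043. The gap is 0.243 − 0.15 = 0.093, and 0.093 / 0.0043 ≈ 22 standard errors. The ratio is 0.243 / 0.15 = 1.6.

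**2. Does the table reproduce?** With S the Kaplan-Meier estimate at 1 year and G the Greenwood sum of 1/[r(r−1)] over events (r = number at risk), the upper bounds are:

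- plain: 1 − S + z·S·√G
- log: 1 − S·exp(−z√G)
- log-log: 1 − S^exp(z√G / −ln S)

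Probability of declaring safety, 200,000 data sets per rate:

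| True rate | 0.05 | 0.10 | 0.15 | 0.20 | 0.25 | 0.30 | 0.35 |
|---|---|---|---|---|---|---|---|
| Plan's table | 0.894 | 0.712 | 0.536 | 0.364 | 0.243 | 0.154 | 0.094 |
| Plain, 85% | 0.884 | 0.706 | 0.524 | 0.366 | 0.242 | 0.154 | 0.092 |
| Log, 85% | 0.887 | 0.711 | 0.532 | 0.374 | 0.249 | 0.159 | 0.096 |
| Log-log, 85% | 0.779 | 0.563 | 0.387 | 0.249 | 0.155 | 0.092 | 0.052 |

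Plain and log match the plan to within 0.012 throughout; log-log does not. Counting zero-event data as not safe drops the plain figure at 0.05 to 0.292, so the table must count them as safe.

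**3. Why the error exceeds 15%.** At a true rate of 0.25 the expected number still at risk at 1 year is 15 × 0.75 × 0.50 × 0.90 = 5.1, too few for a large-sample bound to hold its level. In a separate run of 100,000 data sets, the plain-bound total of 0.245 was made up of 0.055 from data with no events, 0.153 with one and 0.036 with two (parts rounded).

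**4. How often are there no events?** The hazards per year are toxicity −ln(1−p), death 0.693 and withdrawal 0.105. A patient has an observed event within the year with probability q = (toxicity hazard / total hazard) × (1 − e^(−total)).

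- p = 0.05: q = (0.0513/0.8498) × (1 − 0.4275) = 0.0346; no events in 15 patients: (1 − 0.0346)^15 = 0.59.
- p = 0.25: q = (0.2877/1.0862) × (1 − 0.3375) = 0.1755; no events: (1 − 0.1755)^15 = 0.055.

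**5. Can the choice of method change a verdict?** Take a single event with r at risk, so S = 1 − 1/r and √G = 1/√[r(r−1)].

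- r = 8, plain: 0.125 + 1.036 × 0.875 × 0.1336 = 0.246, safe.
- r = 8, log: 1 − 0.875 × e^(−0.1385) = 0.238, safe.
- r = 10, log-log: 1 − 0.9^2.82 = 0.257, not safe.
- r = 11, log-log: 1 − 0.9091^2.82 = 0.236, safe.

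One event with 8, 9 or 10 patients at risk is therefore safe under plain or log and not safe under log-log.

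**6. What would give about 15%?** At a true rate of 0.25, a plain bound gives 0.199 at the 90% one-sided level, 0.174 at 92.5% and 0.155 at 95%. The log-log bound at 85% also gives 0.155 if zero events count as safe; if they do not, it gives 0.100.

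**The case against.** The strongest reply is that nothing is hidden. The 0.25 column is printed a few lines after the 15% statement, the simulation is offered only as a rough guide to power, and taking one minus the confidence level as the error rate is common shorthand. Correcting the label changes no treatment, no data and no outcome of the rule. All of that is true, and it is why the remedy is small. But the text calls 15% the error rate and argues for that value; the table contradicts it without comment.

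Three narrower objections have some force:

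- **Zero events.** Under a plain or log bound, no events gives S = 1, zero variance and an upper bound of 0, so safety follows from the formula. A special rule is needed only for a method such as log-log, where the bound is undefined. This weakens the zero-event point but not the need to name the method.
- **Reproduction.** The match is close, not exact. At a true rate of 0.05 the rerun gives 0.884 (plain) against 0.894, a little over 3 standard errors of the plan's simulation (0.010 / 0.0031). The printed 0.243 does not depend on this.
- **Scope.** The 1 in 4 figure describes the formal rule alone, under the assumed death and withdrawal rates. The review of serious adverse events and the suspension of accrual in Section 11.0, repeated in Section 14.0, operate separately, and the simulation as described does not mention them.

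**Conclusion.** The concern holds. By the plan's own table the type I error of the safety rule is 0.243, about 1.6 times the stated 15%. This needs no assumption beyond reading the 0.25 column. That the table is approximately right and the 15% label wrong rests on a rerun with exponential times and zero-event data counted as safe.

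That the table came from a plain or log Greenwood bound is an inference. The open choice matters: at the same 85% level, the error at the limit runs from about 0.155 (log-log, zero events counted as safe) to about 0.25 (log). Because this is the primary decision rule and the figure is used to justify it, the statement must be corrected.

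**What to change.** **Main change, Section 14.0.** Keep the rule and the table. Replace the type I error sentence with wording such as: The bound has a nominal one-sided level of 15%; in the simulation below, the actual type I error at a true 1-year rate of 0.25 is about 24% (0.243). Then name the interval method used in the simulation and state that data with no events are declared safe, as the table implies.

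*Cost:* two or three sentences, with no change to sample size, data or decision rule. The plan must then justify a less favourable error rate.

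**Optional, only if a true error near 15% is wanted.** Use a plain Greenwood bound at the 95% one-sided level, or a log-log bound at 85% with zero events explicitly counted as safe, and replace the table.

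*Cost:* the probability of declaring safety falls from 0.894 to about 0.78 at a true rate of 0.05, and from 0.712 to about 0.56 at 0.10. No patients are added. This is a trade-off for the sponsor and is not needed to correct the error.

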## 2.1 OBJECTIVES AND SCIENTIFIC AIMS

Primary objective

- To assess the overall toxicity rate at 1 year after whole lung IMRT in this patient population

Secondary objectives

- To determine rates of pulmonary failure-free survival after completion of whole lung IMRT.
- To determine rates of overall survival (OS) after completion of whole lung IMRT.

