### **12.2 Assessment of Secondary Objectives**

### **12.2.1 Assessment of Pulmonary Failure-Free Survival**

A CT scan of the chest will be obtained at 3 and 6 months (+/- 3 weeks) and at 12, 18, and 24 months (+/- 6 weeks) post-treatment. This study will use a modified Response Evaluation Criteria in Solid Tumor (RECIST) for assessment of tumor response. The baseline scan will be the pre-irradiation CT scan.

All patients will be assessed as failure or failure free as defined below. Pulmonary failure-free survival will be defined as survival with no progressive disease in the lungs. CR, PR, and SD will be considered failure-free.

For patients with measurable ( $\geq 5\text{mm}$  but  $<10\text{mm}$ ) lung lesions at the time of study entry:

- a. The investigator will identify up to 5 measurable lung lesions to be followed for response. The sum of the longest diameter (LD) for all target lesions will be calculated and reported as the disease measurement.
- b. Complete response (CR) is defined as the disappearance of all target lesions.
- c. Partial response (PR) is defined as at least a 30% decrease in the disease measurement, taking as reference the pre-irradiation CT scan.
- d. Progressive disease (PD) is defined as at least a 20% increase in the disease measurement, taking as reference the smallest disease measurement recorded since start of treatment, or the appearance of one or more new lung lesions.
- e. Stable disease (SD) is neither sufficient shrinkage to qualify for PR nor sufficient increase to qualify for PD.

For patients with no measurable disease present at baseline:

- a. Stable disease (SD) is defined as no appearance of measurable lesions in the treated area
- b. Progressive disease (PD) is defined as the appearance of measurable lesions on post-treatment scans and will be considered failure-free if no measurable lesions develop.

**12.2.2 Assessment of overall survival** will be performed for each patient using clinical data and information from the social security database.

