### **13.0 CRITERIA FOR REMOVAL FROM STUDY**

If at any time the patient desires to quit participation in the study or if the treating physician determines study participation is no longer appropriate, the patient will be removed from the study.

Toxicity will be evaluated in all patients enrolled who receive any whole-lung irradiation. Pulmonary progression free survival will only be evaluated in patients who complete all radiation treatments and have at least 1 follow-up chest CT.

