Rates of pulmonary failure-free survival will be assessed by cumulative incidence functions. To this end pulmonary failure is the event of interest and other progressions and death are considered as the competing risks. Overall survival rates will be estimated by the Kaplan-Meier method.

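### Pulmonary failure-free survival is defined as survival without lung progression, but the planned cumulative incidence function estimates lung failure as first event, which is a different quantity

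*Combined protocol and SAP*

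**What the plan says.** The secondary objective in Section 2.1 is "To determine rates of pulmonary failure-free survival after completion of whole lung IMRT". Section 12.2.1 gives the definition: "Pulmonary failure-free survival will be defined as survival with no progressive disease in the lungs". It sorts patients by a modified RECIST assessment of the lungs: "CR, PR, and SD will be considered failure-free". No event list in that section names death.

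Section 14.0 names the estimator: "Rates of pulmonary failure-free survival will be assessed by cumulative incidence functions". It then specifies the events: "To this end pulmonary failure is the event of interest and other progressions and death are considered as the competing risks". Overall survival is handled separately by Kaplan-Meier.

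On who is analysed, Section 12.2.1 says "All patients will be assessed as failure or failure free as defined below". Section 13.0, using a slightly different name, says "Pulmonary progression free survival will only be evaluated in patients who complete all radiation treatments and have at least 1 follow-up chest CT". The first follow-up chest CT is due at 3 months, within 3 weeks either side.

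**The concern.** A patient who has died has not survived, so on the plain reading of Section 12.2.1 death ends PFFS. In Section 14.0 death only removes a patient from the risk of lung failure. A non-lung progression does the same, so a later lung progression in that patient is never counted, although Section 12.2.1 makes no such exception. No section reconciles the definition with the estimator.

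PFFS is the trial's only endpoint for lung control. Two analysts could each follow the protocol and report different PFFS rates from the same 15 patients. The treatment of death is not a detail here, because Section 14.0 expects 50% of patients to die within a year without grade 3 toxicity.

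**Working it through.** **No figure to reproduce.** The plan gives no expected rate, precision or power for this endpoint.

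**Step 1: the two quantities.** At time t, everyone alive without lung progression is also free of lung failure as first event. So

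1 − CIF = PFFS + P(died without lung failure) + P(lung failure after another progression).

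The last two terms cannot be negative, so 1 − CIF is at least PFFS. This step needs no assumed rate.

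**Step 2: inputs for the size.** From Section 14.0: 15 patients and 50% death at one year. Rates of lung failure and of other progression are not in the documents, so all values below are assumptions.

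**Step 3: deaths linked to progression.** Assume constant yearly hazards: lung failure l (the same after another progression), other progression o, death d0 before and d1 after any progression. With a = l + o + d0 and b = l + d1, at one year:

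- CIF = (l/a)(1 − e^−a)
- PFFS = e^−a + o(e^−a − e^−b)/(b − a)

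Example with l/o/d0/d1 = 1.0/0.3/0.1/1.0, so a = 1.4 and b = 2.0:

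- CIF = (1.0/1.4)(1 − 0.2466) = 0.538, so 1 − CIF = 0.462.
- PFFS = 0.2466 + 0.3 × (0.2466 − 0.1353)/0.6 = 0.302.
- Gap = 16.0 points.

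| l/o/d0/d1 | One-year mortality | PFFS | 1 − CIF | Gap, points (deaths without lung failure + later lung failures) |
|---|---|---|---|---|
| 1.2/0.1/0.05/1.5 | 0.43 | 0.273 | 0.342 | 6.8 (5.0 + 1.8) |
| 1.5/0.1/0.05/1.5 | 0.48 | 0.203 | 0.265 | 6.3 (4.4 + 1.9) |
| 1.0/0.3/0.1/1.0 | 0.36 | 0.302 | 0.462 | 16.0 (10.7 + 5.3) |
| 0.5/0.3/0.3/1.0 | 0.39 | 0.415 | 0.697 | 28.2 (24.8 + 3.3) |
| 0.7/0.7/0.1/1.5 | 0.46 | 0.335 | 0.637 | 30.2 (22.2 + 8.0) |
| 0.5/0.7/0.3/1.5 | 0.51 | 0.346 | 0.741 | 39.5 (33.5 + 6.0) |

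In the first two rows most deaths follow lung failure. The other four are mixed settings. In patients, 6.8 points is 0.068 × 15 = 1.0, and 16.0 to 39.5 points is 2.4 to 5.9.

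**Step 4: death independent of lung failure.** Let l, d and o be −log(1 − one-year rate). Then CIF = l/(l + d + o) × (1 − e^−(l+d+o)) and PFFS = e^−(l+d). With 50% death:

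| Lung failure | PFFS | 1 − CIF, other progression 0% / 40% | Gap, points |
|---|---|---|---|
| 20% | 0.400 | 0.854 / 0.881 | 45 / 48 |
| 40% | 0.300 | 0.703 / 0.756 | 40 / 46 |
| 60% | 0.200 | 0.545 / 0.620 | 34 / 42 |

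**Step 5: scale of sampling error.** √(p(1 − p)/15) is 0.115 at p = 0.27, 0.122 at 0.34 and 0.126 at 0.40, so about 12 points. The 6 to 7 point gaps lie within this and the others do not.

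**Step 6: the follow-up-CT condition.** Suppose patients who die before 3 months have no CT. In the six settings of step 3 these are 5.4% to 10.7% of patients. Dropping them divides PFFS by the share alive at 3 months and raises it by 1.5 to 4.1 points. If death is independent, the rise is about 2 to 8 points. For example, with 50% death the share alive at 3 months is 0.5^0.25 = 0.841, and 0.400/0.841 = 0.476. The plan's own 1 − CIF moves by only −1.4 to +0.6 points in the six settings.

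**The case against.** The strongest reply is that the analysis is fully specified and only its label is off. Section 14.0 states the event and the competing risks openly, the response rules in Section 12.2.1 never make death a failure, and mortality is reported separately as overall survival. Much of this stands. The CIF is a sound estimate of what it targets, and a rename alone would cure the mismatch. It does not remove the point, because both the objective and the definition name survival, and the stated analysis does not deliver it.

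A reader might infer that the trial will publish an inflated survival rate. The documents do not say that 1 − CIF will be reported as survival, so the favourable bias arises only if someone reads it that way.

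A reader might also infer that Sections 12.2.1 and 13.0 flatly contradict each other on the analysis set. The sentence about all patients can be read as introducing the two response subgroups, with and without measurable disease at baseline, which leaves Section 13.0 as the specific evaluability rule. Its requirement that radiation be completed agrees with the objective. The CT condition names no time point, and its effect on the planned CIF is negligible. It is a side note that matters mainly if PFFS itself is estimated.

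Finally, the hazards are chosen, not sourced. That is correct: the figures illustrate the size, and no single value or upper limit should be read from them.

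**Conclusion.** The mismatch between the definition in Section 12.2.1 and the estimator in Section 14.0 is real and follows from the text alone. Carried out exactly as written, the plan yields the probability of lung failure as first event, not PFFS.

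The direction is certain in population terms: 1 − CIF is never below PFFS. The size is not known. It depends mainly on how many patients die without lung failure and, to a lesser extent (2 to 8 points in the linked settings), on lung failures after another progression. The range runs from about one patient in 15 to nearly half the cohort. Its upper end needs death to be independent of lung failure, which is an extreme assumption.

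The plan should be corrected, but the consequence is bounded. The endpoint has no hypothesis, threshold or decision rule, and nothing here affects the one-year toxicity rule, the 15 patients or the overall survival analysis.

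**What to change.** Choose one of two routes.

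**A. Keep PFFS.** Estimate it by Kaplan-Meier from completion of whole lung irradiation, in all patients who complete it, with lung progression or death from any cause as the event. State a censoring rule for missing lung status. Report the CIF separately as cumulative incidence of pulmonary failure, and say whether lung failure after another progression counts. Drop the follow-up-CT condition of Section 13.0 from this main analysis, because it removes patients who die before their first scan. The CT-evaluable set can serve as a sensitivity analysis.

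**B. Keep the CIF.** Rename the endpoint cumulative incidence of pulmonary failure in Sections 2.1, 12.2.1, 13.0 and 14.0.

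Under either route use one name throughout; Section 13.0 currently speaks of progression where the other sections speak of failure.

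**Cost.** Route B is wording only, but the trial then no longer reports PFFS. Route A changes the estimator and the analysis set, gives a less favourable rate than 1 − CIF and overlaps with overall survival. It also needs lung status after a non-lung progression. Chest CTs are already scheduled to 24 months, although patients removed from study may miss them. Deaths are already collected: under Section 12.2.2 the survival assessment "will be performed for each patient using clinical data and information from the social security database".
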